8.3 Risks and/or Benefits to Subjects

The dose of LOXO-292 administered in this study is not anticipated to induce any potential risk or benefit to subjects participating in this study as it is a single dose which does not exceed the highest dose safely administered in first in human studies [Investigator's Brochure 2018]. The dose of itraconazole and rifampin administered in this study is not anticipated to induce any potential risk or benefit to subjects participating in this study, as they are multiple doses administered according to the dosing recommendations [itraconazole capsules; Mylan Company Inc., rifampin capsules; Lannett Company Inc.] and have been administered safely at the current dosing regimen in previous clinical studies [Templeton al., 2011; Ke et al., 2014; Tortorici et al., 2014; and Tran et al., 1999].

The safety monitoring practices employed by this protocol (i.e., 12-lead ECG, physical examinations, vital signs, clinical laboratory tests, and AE questioning) are adequate to protect the subjects' safety. In addition, as an inhibitory effect is anticipated in Part 1 of the study and LOXO-292 exposure levels are expected to be increased when coadministered with multiple-dose itraconazole, Part 1 was planned with a sentinel group where only 3 subjects will first receive the dose of 160 mg LOXO-292 with and without itraconazole. Following

review of all pertinent safety and tolerability data, a decision will be made to either continue Part 1 for the remaining subjects and to confirm the dose.

There will be no direct health benefit for study participants from receipt of study drug. An indirect health benefit to the healthy subjects enrolled in this study is the free medical tests received at screening and during the study.

9 OBJECTIVES AND ENDPOINTS

9.1 Objectives

Part 1 (Itraconazole):

Primary:

To investigate the effect of multiple-dose itraconazole, a strong CYP3A4 and P-gp inhibitor, on the single dose PK of LOXO-292 in healthy adult subjects.

Secondary:

To determine the safety and tolerability of a single dose of LOXO-292 alone and coadministered with multiple doses of itraconazole in healthy adult subjects.

Part 2 (Rifampin):

Primary:

To investigate the effect of single-dose rifampin, a P-gp inhibitor, and multiple-dose rifampin, a strong CYP3A4 and P-gp inducer, on the single dose PK of LOXO-292 in healthy adult subjects.

Secondary:

To determine the safety and tolerability of a single dose of LOXO-292 alone and coadministered with single and multiple doses of rifampin in healthy adult subjects.

9.2 Endpoints

Pharmacokinetics:

Part 1 (Itraconazole):

The PK endpoints will include AUC_{0-t}, AUC_{0-inf}, AUC%extrap, Cmax, Tmax, Kel, CL/F, and t_{1/2} for LOXO-292 administered with and without interacting drug itraconazole.

Part 2 (Rifampin):

The PK endpoints will include AUC_{0-t}, AUC₀₋₂₄ (Day 1 PK only), AUC_{0-inf}, AUC%extrap, Cmax, Tmax, Kel, CL/F, and t_{1/2} for LOXO-292 administered with and without interacting drug rifampin.

Safety:

Parts 1 and 2:

Safety endpoints will include 12-lead ECGs, physical examinations, vital signs, clinical laboratory tests, and AEs for both parts.

10 STUDY DESIGN

10.1 Overall Study Design and Plan

This is a 2-part study. Each part will be conducted as an open label, 2-period, fixed-sequence study. Study parts may be conducted concurrently. Subjects will only participate in one study part.

CCI [REDACTED] healthy, adult male and female (women of non-childbearing potential only) subjects will be enrolled in total; CCI [REDACTED] to each study part (Parts 1 and 2). Every attempt will be made to enroll at least 4 subjects of each sex in each study part.

Screening of subjects will occur within 28 days prior to the first dosing.

Part 1 (Itraconazole):

On Day 1 of Period 1, a single oral dose of LOXO-292 will be administered followed by PK sampling for 168 hours.

In Period 2, an oral dose of itraconazole will be administered QD for 11 consecutive days (Day -4 to Day 7) with a single oral dose of LOXO-292 coadministered on Day 1. Pharmacokinetic sampling for LOXO-292 will be taken for 168 hours following LOXO-292 dosing on Day 1.

A CCI [REDACTED] will initiate Part 1; all subjects will receive a single dose of LOXO-292 on Day 1 of both periods. Following collection of the last PK sample in Period 2, the PI, in consultation with the Sponsor, will review all pertinent safety and tolerability data before proceeding to dose the remaining subjects.

Interim PK will be provided after completion of the sentinel group but it is not required for the dose selection of the remaining subjects.

There will be a washout period of at least 7 days between the dose in Period 1 and the first dose (i.e., itraconazole) in Period 2.

Safety will be monitored throughout the study.

Timing of all study procedures are indicated in the Study Events Flow Chart (Section 6, Table 1)

Part 2 (Rifampin):

On Day 1 of Period 1, a single oral dose of LOXO-292 will be administered followed by PK sampling for 168 hours.

In Period 2, an oral dose of rifampin will be administered QD for 16 consecutive days (Days 1 to 16) with a single oral dose of LOXO-292 coadministered on Day 1 and Day 10.

Pharmacokinetic sampling for LOXO-292 will be taken for 24 hours following LOXO-292 dosing on Day 1 and for 168 hours following LOXO-292 dosing on Day 10.

Morning urine will be collected on Days 1, 4, 8, and 10 of Period 2 (and will be stored for future potential assessment of 6 β -hydroxycortisol and free cortisol concentrations to evaluate the level of CYP3A enzyme induction).

There will be a washout period of at least 7 days between the dose in Period 1 and the first dosing (i.e., rifampin and LOXO-292) in Period 2.

Safety will be monitored throughout the study.

Timing of all study procedures are indicated in the Study Events Flow Chart ([Section 6, Table 2](#))

In both study parts, subjects may be replaced at the discretion of the Sponsor.

10.1.1 Confinement, Return Visits, and Follow-Up

Part 1 (Itraconazole):

Subjects will be housed on Day -1 of Period 1, at the time indicated by the CRU until after the last PK blood draw and/or study procedures scheduled on Day 8 of Period 2 as indicated in the Study Events Flow Chart ([Section 6](#)).

Part 2 (Rifampin):

Subjects will be housed on Day -1 of Period 1, at the time indicated by the CRU, until after the last PK blood draw and/or study procedures scheduled on Day 17 of Period 2 as indicated in the Study Events Flow Chart ([Section 6](#)).

Parts 1 and 2 (see [Table 1](#) and [Table 2](#)):

Subjects are confined throughout the washout period.

At all times, a subject may be required to remain at the CRU for longer at the discretion of the PI or designee.

The CRU will contact all subjects who received at least one dose of study drug (including subjects who terminate the study early) using their standard procedures (i.e., phone call or other method of contract) approximately 7 days after the last study drug administration to determine if any AE has occurred since the last study visit.

10.1.2 End of Study Definition

The end of study is defined as the date of the last scheduled study procedure as outlined in the Study Events Flow Chart ([Section 6](#)).

11 STUDY POPULATION

The Sponsor will review medical history and all screening evaluations for potential subjects prior to enrollment. The Sponsor will provide approval of subjects for enrollment prior to dosing.

11.1 Inclusion Criteria

Subjects must fulfill all of the following inclusion criteria to be eligible for participation in the study:

1. Healthy, adult, male or female (of non-childbearing potential only), 18 to 55 years of age, inclusive, at screening.
2. Continuous non-smoker who has not used tobacco- and/or nicotine-containing products for at least 3 months prior to the first dosing and throughout the study, based on subject self-reporting.
3. Body mass index (BMI) ≥ 18.0 and $\leq 32.0 \text{ kg/m}^2$ and have a minimum weight of at least 50 kg at screening.
4. Medically healthy with no clinically significant medical history, physical examination, laboratory profiles, vital signs, or ECGs, as deemed by the PI or designee, and as confirmed by the Sponsor. Liver function tests (alanine aminotransferase [ALT], aspartate aminotransferase [AST], alkaline phosphatase [ALP]), and serum (total and direct) bilirubin, as well as amylase and lipase, must be within the upper limit of normal for the laboratory used by the clinical site at screening and check-in (Day -1 Period 1 of each study Part). Rechecks of the liver function tests (ALT, AST, and ALP) and serum (total and direct) bilirubin, as well as amylase and lipase will be permitted up to two times to confirm subject eligibility. Subjects may be eligible for participation in the study based on rechecked values if the PI (or designee), with agreement from the Sponsor, feels that the results are not clinically significant, and will not impact study conduct.
5. A female must be of non-childbearing potential and have undergone one of the following sterilization procedures at least 6 months prior to the first dosing:
 - hysteroscopic sterilization;
 - bilateral tubal ligation or bilateral salpingectomy;
 - hysterectomy;
 - bilateral oophorectomy;or be postmenopausal with amenorrhea for at least 1 year prior to the first dosing and follicle-stimulating hormone (FSH) serum levels consistent with postmenopausal status.
6. A non-vasectomized, male subject must agree to use a condom with spermicide or abstain from sexual intercourse during the study until 6 months after the last dosing. (No restrictions are required for a vasectomized male provided his vasectomy has been

performed 4 months or more prior to the first dosing of study drug. A male who has been vasectomized less than 4 months prior to study first dosing must follow the same restrictions as a non-vasectomized male).

7. If male, must agree not to donate sperm from the first dosing until 6 months after the last dosing.
8. Understands the study procedures in the informed consent form (ICF), and be willing and able to comply with the protocol.

11.2 Exclusion Criteria

Subjects must not be enrolled in the study if they meet any of the following criteria:

1. Is mentally or legally incapacitated or has significant emotional problems at the time of the screening visit or expected during the conduct of the study.
2. History or presence of clinically significant medical or psychiatric condition or disease in the opinion of the PI or designee, and as confirmed by the Sponsor.
3. History of any illness that, in the opinion of the PI or designee, and as confirmed by the Sponsor, might confound the results of the study or poses an additional risk to the subject by their participation in the study.
4. Have a history of gastritis, gastrointestinal tract or hepatic disorder or other clinical condition that might, in the opinion of the PI or designee, and as confirmed by the Sponsor, affect the absorption, distribution, biotransformation, or excretion of LOXO-292, itraconazole, or rifampin.
5. History or presence of alcoholism or drug abuse within the past 2 years prior to the first dosing.
6. History or presence of hypersensitivity or idiosyncratic reaction to the study drugs or related compounds, or inactive ingredients.
7. History or presence of:
 - liver disease,
 - diabetes,
 - pancreatitis,
 - peptic ulcer disease,
 - intestinal malabsorption,
 - gastric reduction surgery,
 - history or presence of clinically significant cardiovascular disease:

- myocardial infarction or cerebrovascular thromboembolism within 6 months prior to first dosing
- symptomatic angina pectoris
- New York Heart Association Class ≥ 2 congestive heart failure
- congenital prolonged QT syndrome
- ventricular pre-excitation syndrome (Wolff-Parkinson White syndrome)
- arrhythmia or history of arrhythmia requiring medical intervention
- ventricular dysfunction or risk factors for Torsades de Pointes (eg heart failure, cardiomyopathy, family history of Long QT Syndrome)
- significant screening ECG abnormalities:
 - Left bundle-branch block
 - Second degree atrioventricular (AV) block, type 2, or third degree AV block
 - QTcF interval is >460 msec (males) or >470 msec (females)
 - ECG findings deemed abnormal with clinical significance by the PI or designee at screening and prior to Day 1 dosing of Period 1.

8. Female subjects of childbearing potential or lactating.
9. Female subjects with a positive pregnancy test.
10. Positive urine drug or alcohol results at screening or check-in.
11. Positive results at screening for human immunodeficiency virus (HIV), hepatitis B surface antigen (HBsAg) or hepatitis C virus (HCV).
12. Seated blood pressure is less than 90/50 mmHg or greater than 139/89 mmHg at screening and prior to Day 1 dosing of Period 1. Rechecks of blood pressure values will be permitted up to two times to confirm eligibility for study participation. Subjects may be eligible for participation in the study based on rechecked values if the PI (or designee), with agreement from the Sponsor, feels that the results are not clinically significant, and will not impact study conduct.
13. Seated heart rate is lower than 50 bpm or higher than 99 bpm at screening and prior to Day 1 dosing of Period 1. Rechecks of heart rate values will be permitted up to two times to confirm eligibility for study participation. Subjects may be eligible for participation in the study based on rechecked values if the PI (or designee), with agreement from the Sponsor, feels that the results are not clinically significant, and will not impact study conduct.
14. Unable to refrain from or anticipates the use of:
 - Any drug, including prescription and non-prescription medications, herbal remedies, and vitamin supplements, beginning 14 days prior to the first dosing and throughout the study. After first dosing, acetaminophen (up to 2 g per 24 hours) may be administered at the discretion of the PI or designee.

- Any drugs known to be significant inducers of CYP3A enzymes and/or P-gp, including St. John's Wort, for 28 days prior to the first dosing and throughout the study. Appropriate sources (e.g., Flockhart TableTM) will be consulted to confirm lack of PK/pharmacodynamic interaction with study drug.

15. Has been on a diet incompatible with the on-study diet, in the opinion of the PI or designee and as confirmed by the Sponsor, within the 30 days prior to the first dosing and throughout the study.

16. Donation of blood or significant blood loss within 56 days prior to the first dosing.

17. Plasma donation within 7 days prior to the first dosing.

18. Participation in another clinical study within 30 days prior to the first dosing. The 30-day window will be derived from the date of the last blood collection or dosing, whichever is later, in the previous study to Day 1 of Period 1.

19. For Part 2, estimated creatinine clearance < 90 mL/min at screening or on Day -1 of Period 1.

20. For Part 1, history or presence of uncorrected hypokalemia (potassium levels < 3.7) and/or hypomagnesemia (magnesium levels < 1.9) as deemed clinically significant by the PI or designee, and as confirmed by the Sponsor.

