8.1.3 Rifampin

Rifampin is a semi-synthetic antibiotic derivative of rifamycin SV which acts by inhibiting deoxyribonucleic acid (DNA)-dependent ribonucleic acid (RNA) polymerase activity in susceptible species of *Mycobacterium tuberculosis*. Its activity does not impede mammalian enzyme RNA polymerase, therefore it is an effective treatment for both tuberculosis and meningococcus infections.

After oral administration, rifampin is readily absorbed from the gastrointestinal tract and is considered to be a highly variable drug in healthy adults and pediatric populations. Gastric absorption with food reduces the bioavailability of rifampin by about 30%. Concomitant antacid administration may also reduce the absorption of rifampin. Thus, daily doses of rifampin should be given at least 1 hour before the ingestion of antacids, and 1 hour before or 2 hours after a meal.

Rifampin is widely distributed throughout the body and can reach effective concentrations in various organs and cerebrospinal fluid. Rifampin is 80% protein bound in the blood while the remaining unbound fraction is not ionized and can readily diffuses into tissues.

In healthy adults, the mean biological $t_{1/2}$ of rifampin in serum averages 3.35 ± 0.66 hours after a 600 mg oral dose, with increases up to 5.08 ± 2.45 hours reported after a 900 mg dose. With repeated administration, the $t_{1/2}$ decreases and reaches average values of approximately 2 -3 hours. The half-life does not differ in patients with renal failure at doses not exceeding 600mg daily, and consequently, no dosage adjustment is required. After a single 900 mg oral dose of rifampin in patients with varying degrees of renal insufficiency, the mean $t_{1/2}$ increased from 3.6 hours in healthy adults to 5.0, 7.3, and 11.0 hours in patients with glomerular filtration rates of 30 to 50 mL/min, less than 30 mL/min, and in anuric patients, respectively.

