8.2.2 Rationale for the Dose Selection and Dosing Regimen

LOXO-292:

A single dose of 160 mg LOXO-292 was selected because is a dose that has been given twice daily to cancer patients and preliminary safety and PK data show that this dose is likely at or near a recommended Phase 2 dose for further study in cancer patients. A single dose of 160 mg should provide sufficient levels of LOXO 292 to assess the PK properties being investigated.

LOXO-292 is a substrate of CYP3A4 and thus there may be an increase in the exposure (AUC) of LOXO-292 when it is given with the CYP3A4 inhibitor itraconazole. However, even if CYP3A4 is inhibited, LOXO-292 is expected to be eliminated from the body because LOXO-292 is also eliminated by renal excretion and renal excretion of LOXO-292 is unlikely to be affected by CYP3A4 inhibition. Renal clearance of LOXO-292 (as unchanged drug) is being evaluated in study LOXO-RET-17001. Interim analysis of data from 48 subjects in that study shows that a mean of approximately 8.4% of the oral dose was recovered in the urine as unchanged LOXO-292 (data on file, Loxo Oncology). Therefore, in the unlikely event that LOXO-292 were 100% absorbed and bioavailable, and its clearance were 100% inhibited by itraconazole, the body could clear the drug renally. Furthermore, as of a January 5, 2018 data cut-off date, safety data were available from 57 patients with doses up to 160 mg BID (320 mg/day). As of this date, no dose-limiting toxicities have been reported.

Itraconazole:

The clinical dose of itraconazole is 200 mg administered QD. In this study, itraconazole will be dosed for 11 days (Day -4 to Day 7), with LOXO-292 coadministered on the fifth day of itraconazole dosing. Although, itraconazole reaches steady-state at approximately 15 days QD dosing, similar dosing schemes have been used in previously reported DDI studies and have demonstrated sufficient inhibition of CYP3A enzymes with 5 days of QD dosing [Yoshizato et al., 2012]. To maintain the same level of inhibition, itraconazole will be administered throughout PK sampling of LOXO-292 until Day 7.

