13.2.5 Clinical Laboratory Tests

All tests listed below will be performed as outlined in the Study Events Flow Chart (Section 6). In addition, laboratory safety tests may be performed at various unscheduled time points, if deemed necessary by the PI or designee.

Hematology

- Hemoglobin
- Hematocrit
- Total and differential leukocyte count
- Red blood cell count
- Platelet count

Coagulation

- Prothrombin Time/International normalized ratio
- Activated partial thromboplastin time

Serum Chemistry*

- Blood Urea Nitrogen
- Bilirubin (total and direct)
- Alkaline phosphatase
- Aspartate aminotransferase
- Alanine aminotransferase
- Albumin
- Sodium
- Potassium
- Magnesium
- Chloride
- Glucose (fasting)
- Creatinine**
- Cholesterol
- Triglycerides
- Phosphorus
- Creatine kinase
- Amylase
- Lipase

Urinalysis

- pH
- Specific gravity
- Protein***
- Glucose
- Ketones
- Bilirubin
- Blood***
- Nitrite***
- Urobilinogen
- Leukocyte esterase***

Additional Tests

- HIV test
- HBsAg
- HCV
- Urine drug screen
 - Opiates
 - Opioids (methadone, oxycodone, and fentanyl)
 - Amphetamines
 - Barbiturates
 - Benzodiazepines
 - Cocaine
 - Cannabinoids
- Urine alcohol screen
- Serum pregnancy test (for females only)
- FSH (for postmenopausal females only)
- Thyroid stimulating hormone

* Serum chemistry tests will be performed after at least a 12-hour fast at screening (Parts 1 and 2) and at check-in; at other scheduled times, serum chemistry tests will be performed after at least an 8-hour fast. However, in case of dropouts or rechecks, subjects may not have fasted for 12 or 8 hours prior to the time that the serum chemistry sample being taken.

** At screening both study parts and on Day -1 of Period 1, Part 2, creatinine clearance will be calculated using the Cockcroft-Gault formula.

*** If urinalysis is positive for protein, blood, nitrite and/or leukocyte esterase, a microscopic examination (for red blood cells, white blood cells, bacteria, casts, and epithelial cells) will be performed.

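### Does limiting the creatinine clearance exclusion to Part 2 undermine the renal-elimination argument made for Part 1?

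*Protocol*

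**What the plan says.** Section 8.2.2 of the protocol expects LOXO-292 exposure to rise with itraconazole and reasons that "even if CYP3A4 is inhibited, LOXO-292 is expected to be eliminated from the body because LOXO-292 is also eliminated by renal excretion". It reports that "a mean of approximately 8.4% of the oral dose was recovered in the urine as unchanged LOXO-292", from an interim analysis of 48 subjects. It then takes an extreme case, labelled unlikely, of complete bioavailability: if "its clearance were 100% inhibited by itraconazole, the body could clear the drug renally". It adds a second support: safety data from 57 patients at doses up to 160 mg BID, with no dose-limiting toxicity.

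Section 8.3 says the LOXO-292 dose is not expected to pose a risk because it "does not exceed the highest dose safely administered in first in human studies". The same section expects higher exposure with itraconazole and gives that as the reason for a sentinel group of 3.

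The only numeric renal criterion is exclusion 19 in Section 11.2: "For Part 2, estimated creatinine clearance < 90 mL/min at screening or on Day -1 of Period 1". On rifampin itself, Section 8.1.3 says "The half-life does not differ in patients with renal failure at doses not exceeding 600mg daily". Section 13.2.5 states "At screening both study parts and on Day -1 of Period 1, Part 2, creatinine clearance will be calculated" by Cockcroft-Gault.

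**The concern.** The criterion appears to be attached to the wrong part. Renal excretion is the fallback route in Part 1, where exposure is expected to rise. The numeric limit applies in Part 2, where multiple-dose rifampin should lower exposure and where, by the protocol's own account, renal function does not alter rifampin's half-life at the dose used. No reason is given. The Part 1 screening value is calculated, but no numeric rule uses it.

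The rationale also invokes a worst case without sizing it. Saying that the body could clear the drug renally is true but silent on how slowly, and Section 8.3 compares nominal doses although exposure is what itraconazole changes. If healthy-volunteer safety in Part 1 really rested on an unprotected and unsized route, the sponsor would need to correct the eligibility text and the risk statement.

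**Working it through.** **Inputs.** Urinary recovery of unchanged drug, 0.084 of the oral dose (8.2.2). Half-life of at least 12 h and possibly 30 h (8.2.1). Study dose 160 mg. Highest patient regimen cited, 320 mg/day (8.2.2). The protocol states no exposure multiple, so there is no figure to reproduce.

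**Bounding AUC ratio.** AUC = Ae/CLr, where Ae is the amount excreted unchanged in urine and CLr is renal clearance. At baseline Ae = 0.084 × dose. In the extreme case bioavailability (F) is 1 and only the renal route remains, so Ae = 1 × dose. With CLr unchanged:

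- ratio = 1/0.084 = 11.9, whatever the baseline F.

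**How far that depends on the extreme assumptions.**

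- If F stays at its baseline value, the ratio is F/0.084: 6.0 at F = 0.5, 8.3 at F = 0.7, 10.7 at F = 0.9 (F values assumed).
- If true urinary recovery were 6% to 20% (assumed range), 1/recovery runs from 16.7 to 5.0. The collection interval is not stated; incomplete collection would mean true recovery above 8.4% and a smaller ratio.
- With 90% of non-renal clearance blocked and baseline F = 1: 1/(0.084 + 0.1 × 0.916) = 1/0.1756 = 5.7.

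**Half-life.** The renal share of clearance is 0.084/F, so with unchanged volume and only renal clearance left, half-life is multiplied by F/0.084, with F at baseline. If baseline F = 1, 12 to 30 h becomes 12/0.084 = 143 h to 30/0.084 = 357 h. If baseline F = 0.5 (assumed), it becomes about 71 to 179 h. The longer figures therefore need complete bioavailability at baseline, which the documents do not give.

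**Scale against patient exposure.** 160/0.084 = 1,905 mg, the dose that would give the same total AUC at baseline clearance. 1,905/320 = 5.95, or about 6 days of the 160 mg BID regimen. This assumes dose-proportional kinetics and similar clearance in patients and volunteers.

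**Sensitivity to renal function.** Assume CLr is proportional to creatinine clearance and compare 60 with 90 mL/min. With only renal clearance left, AUC is 90/60 = 1.5 times higher. Without inhibition it is 1/(0.916 + 0.084 × 60/90) = 1.03 times higher. Renal function does matter more in the extreme case, but nothing in the documents suggests that a subject with such a value would be approved.

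**What protects Part 1.** The following apply to both parts:

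- renal function tests at screening (13.1) and creatinine clearance at screening (13.2.5);
- Sponsor review of all screening evaluations and approval before dosing (Section 11);
- no clinically significant laboratory findings (inclusion 4);
- exclusion for conditions judged to affect LOXO-292 excretion (exclusion 4);
- age 18 to 55, no diabetes, and a blood pressure ceiling.

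Part 1 also has the sentinel group, whose review covers safety and tolerability data and may lead to a reduced LOXO-292 dose (12.2). What Part 1 lacks is a numeric cut-off.

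**The case for a change.** The strongest case for a change is this. The argument in 8.2.2 concerns Part 1 alone, the criterion covers Part 2 alone, and 8.1.3 removes the most obvious reason for that choice. Section 8.1.1 says metabolism is mainly by CYP3A4 and reports a steep dose response for moribundity and death in both toxicology species, so strong inhibition is not far-fetched and the multiple deserves stating. The sentinel review follows the 168 h sample, which in the extreme case with baseline F = 1 is only 168/357 = 0.5 to 168/143 = 1.2 half-lives, and interim PK is not required for the dose decision. The nominal-dose comparison in 8.3 cannot carry the conclusion placed on it.

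Part of this stands. The scope of criterion 19 is unexplained, and 8.3 would be better argued on exposure. But the protocol does not rest on the renal route alone: patient experience and the sentinel design are separate supports, and the sentinel review is based on observed safety and tolerability, not on nominal dose. Section 8.3 states openly that exposure should rise. Section 8.2.2 claims only that a route of elimination remains; it asserts neither a normal rate nor an exposure limit, so criterion 19 does not contradict it. Part-specific criteria are not unusual here: criterion 20, on potassium and magnesium, applies to Part 1 only.

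**Conclusion.** No change to the plan is needed. The arithmetic is right: 8.4% recovery implies a total AUC ratio of up to 11.9 in the protocol's extreme case. That figure bounds total AUC after one dose. It is not a forecast or a Cmax ratio, and it falls to 6.0 to 10.7 if F stays at an assumed 0.5 to 0.9. It rests on unchanged renal clearance and on an interim patient mean with no stated collection interval. On a total-AUC basis it corresponds to about 6 days at the highest patient regimen cited.

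Printing the multiple in 8.2.2 or 8.3 would improve the rationale but alter no endpoint, model or comparison, and each subject serves as their own control. The wording of criterion 19 is clear about its scope, so asking whether it covers Part 1 only seeks an explanation of something already stated. In Part 1 the gap is filled by individual screening, Sponsor approval and the sentinel step. Why the numeric limit is confined to Part 2, given Sections 8.1.3, 8.2.2 and 13.2.5, is a reasonable query to the sponsor. Whether any renal limit belongs in Part 1 is the sponsor's clinical decision, and this review takes no position on it.
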